#### 3.0 Intervention to be studied

Moodivate. Details of Moodivate are provided in the "Progress Report" section above. Participants randomized to the Moodivate condition will be instructed to utilize Moodivate regularly, at least once per day, for the treatment of depressed mood.

Moodivate + EHR Provider Portal. Participants randomized to the Moodivate + EHR condition will receive similar instructions as those randomized to Moodivate, but will also be instructed that their PCP will have access to metrics related to their app utilization and may choose to follow-up with them regarding treatment utilization and response. The PCP for each participant randomized to this condition will be provided EHR access to Moodivate metrics. Portal design will be developed iteratively with providers as part of Aim 1, but we expect that it will include metrics related to change in mood, frequency of app utilization, and frequency of activity completion.

TAU. TAU is designed to mimic existing standard treatment for depression. Participants in all conditions, including TAU, will be provided educational material about mood management available via the EHR with the suggestion to discuss questions with their PCP. Across conditions, participants will not be precluded from obtaining additional treatment (medication or psychotherapy), which will be tracked as a study outcome.

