# Aim 2: RCT of Moodivate vs. Moodivate + EHR Provider Portal vs. TAU within Primary Care. Procedures

After completing determination of eligibility and consent, the participant will complete baseline assessments remotely and be randomized via REDCap 1:1:1 to Moodivate, Moodivate + EHR, or TAU. Participants will be randomized via a mixed block design stratified by baseline depressive symptoms and concurrent depression treatment. If randomized to either of the Moodivate conditions, study staff will provide the participant with an app download code and will ensure successful download. Study staff will then give the participant a brief, scripted overview (as utilized in our Phase I trial) regarding app utilization and will provide the participant with 10 minutes to use the app and ask questions. Participants randomized to the Moodivate + EHR condition will be told that their PCP will be provided information regarding their Moodivate utilization and may discuss use and response during their next visit. Providers of Moodivate + EHR patients will be granted access to the EHR provider portal **for those patients** and it will be suggested that they review the portal during the patient's next visit. The provider portal will be developed such that it is available for providers to view only if the patient is randomized to the Moodivate + EHR condition.

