# **Data Analytic Plan for Aim 2**

Efficacy. Descriptive statistics (means, SDs, frequencies, percentages) will be calculated and compared for overall group differences via chi-square tests, ANOVA models, or nonparametric equivalents, as necessary, for baseline variables. Pairwise differences will be explored for variables that show a significant overall group difference. Significant baseline demographic differences between groups will be included as covariates in regression analyses. Generalized Estimating Equation (GEE) modeling will be used to examine group differences (Moodivate, Moodivate + EHR, TAU) in depression (BDI-II) over time along with the interaction between group and time adjusting for baseline differences and baseline depression. All models will include a clustering effect to account for the clinic from which the participant was recruited. Sex will be included as a covariate in all models. GEE affords examination of specific contrasts (i.e., Moodivate vs. TAU at a specific time point) as well as overall effects of group, time, and the interaction between group and time, while also accounting for repeated measures within participants and any clustering within clinics.

Missing Data. Missing data can be a concern in longitudinal studies, and GEE modeling can assist by including participants with partially complete follow-up data instead of requiring complete follow-up data from all participants. All randomized participants will be included in primary analyses, and imputation methods will be used to accommodate missing data if missing data is >10%. For small amounts of missing data (<10%), these data points will be excluded from modeling, as the sample size has been inflated to account for some attrition. Additionally, sensitivity analyses will be done using only participants with complete follow-up data, with results compared to primary analyses. Attrition will also be assessed to determine whether dropout is differential by group to identify any potential bias in group assignment.

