Even if the app is not cost-saving, there is a compelling case for adoption if the intervention improves outcomes cost-effectively. For cost-effectiveness analyses, we will follow gold standard procedures and calculate the incremental cost effectiveness ratio (ICER), defined as the additional cost per additional outcome desired. Because there are three groups, we will order interventions from most to least costly, likely to be (a) Moodivate + EHR, (b) Moodivate, and (c) TAU. We will then calculate the ICERs for (a) vs. (b) and (b) vs. (c). Because this is an RCT, our ICER is straightforward: (cost of Moodivate + EHR – cost of Moodivate) / (BDI-II score of Moodivate + EHR – BDI-II score of Moodivate). This formula is replaced with corresponding variables when the comparison is Moodivate vs. TAU. We will assume (but verify) that the three groups have similar characteristics so that observed differences in outcomes reflect differences in the intervention. If group differences are evident, a generalized linear model will be used to adjust for between-groups differences. Any intervention that is "dominated" (i.e., is more expensive but yields less desirable result) will be eliminated from consideration. Likewise, we will also eliminate any intervention that is "extendedly dominated" (i.e., an intervention that has an ICER higher than the next most effective intervention). For example, if the ICER of Moodivate vs. TAU is higher than the ICER of Moodivate + EHR vs. Moodivate, we will eliminate Moodivate as being extendedly dominated and calculate the ICER of Moodivate + EHR versus TAU directly. All costs will be converted to net present value at standard discount rates (3% and 5%). Probabilistic sensitivity analyses using Monte Carlo microsimulations will test the robustness of results with differing ranges of costs and treatment effectiveness. Ranges will be based on confidence intervals estimated in Aim 2 outcomes. For cost data, MPT will estimate ranges of app development and distribution costs. An acceptability curve of the costeffectiveness of any non-dominated intervention will demonstrate the probability of app cost-effectiveness under different levels of willingness to pay.

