#### Quality Assurance

Accuracy and completeness of the data collected will be ensured by weekly review. The REDCap system does not accept outliers, illogical response patterns, etc. The PI and research assistant will have weekly meetings to discuss any qualitative comments received during data collection and any problems in data collection. The PI will examine the database for potential irregularities monthly. Initial data analyses will

examine distributions of variable scores and comparability of baseline characteristics across conditions (for Aims 2 and 3) in case analyses need to be adjusted for these. Confidentiality procedures are outlined above.

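### The primary GEE leaves out one randomisation stratum (concurrent depression treatment) and picks further covariates by baseline significance test; SAP wording can fix both

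*Combined protocol and SAP*

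**What the plan says.** Section 10.0 (Aim 2, Procedures) uses 1:1:1 mixed-block randomisation, "stratified by baseline depressive symptoms and concurrent depression treatment".

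Section 11.0 (Data Analytic Plan for Aim 2, Efficacy) models BDI-II by GEE with group and time, "along with the interaction between group and time adjusting for baseline differences and baseline depression". It adds "Sex will be included as a covariate in all models" and a clustering effect for clinic. Baseline variables are first tested for group differences, and then: "Significant baseline demographic differences between groups will be included as covariates in regression analyses". No demographics are listed and no test level is given.

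The same section says of the results to be examined: "GEE affords examination of specific contrasts (i.e., Moodivate vs. TAU at a specific time point) as well as overall effects of group", followed by time and the interaction. It does not say which of these decides the trial.

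Two other places repeat the idea that observed imbalance triggers adjustment. Section 12.0 (Quality Assurance) plans to look at "comparability of baseline characteristics across conditions (for Aims 2 and 3) in case analyses need to be adjusted for these". The Aim 3 analysis plan says "If group differences are evident, a generalized linear model will be used to adjust for between-groups differences".

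Concurrent depression treatment is not named as a covariate in any analysis section. Treatment obtained during the trial is a different variable: section 3.0 allows participants "obtaining additional treatment (medication or psychotherapy), which will be tracked as a study outcome".

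**The concern.** There are two linked weaknesses in the primary model.

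- **The screen.** In a randomised trial, a significant baseline difference is a chance event. Choosing covariates that way takes in variables whether or not they predict BDI-II, and passes over prognostic ones that happen to be balanced. With no list and no threshold, two analysts following the text could fit different primary models.
- **The missing stratum.** Stratified blocks lower the true sampling variance of the treatment contrast if the stratum is prognostic. A model without the stratum does not recognise that reduction, so its reported standard error is too wide and the test is slightly conservative. The design benefit is paid for but not used.

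At stake are the prespecification of the primary model and, depending on how prognostic concurrent treatment is, some power for group contrasts.

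**Working it through.** **1. Can the screen bring the stratum in?** By its wording it covers demographics only, and concurrent treatment is not one. Even on a wider reading, stratified blocks keep it balanced. In 4,000 simulated trials of 600 participants, with stratified blocked 1:1:1 randomisation, it was never significant at baseline.

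**2. What does the screen admit?** With k independent demographics tested at an assumed level of 0.05, the chance that at least one enters by chance alone is 1 − 0.95^k:
- k = 3: 14%
- k = 5: 23% (also 23% in the simulation)
- k = 10: 40%

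The plan gives neither k nor the test level; both are assumptions.

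**3. Inputs for the precision cost** (section 11.0, Sample Size Estimation):
- Decreases of 12.2 (SD 13.2) and 7.8 (SD 15.0), so the difference is 4.4.
- Pooled SD = √((13.2² + 15.0²)/2) = 14.13, so d = 4.4/14.13 = 0.311.
- Two-sided α = 0.025, so the critical z is 2.241.
- Analysed per arm: 695/3 × 0.8 ≈ 185, or 200 × 0.8 = 160.

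The plan's own figure, 158 per group for 80% power, does not reproduce. A t-test at α = 0.025 needs 198, and 158 gives power of about 0.70. That is a separate matter. Here only the differences in power are used.

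**4. Formulas.** Let R² be the share of the residual variance of the contrasted outcome, beyond baseline BDI-II, that concurrent treatment explains. The documents do not give it, so a range is assumed.
- Excess SE = 1/√(1−R²) − 1
- Power, stratum omitted = Φ[(d√(n/2) − 2.241)/√(1−R²)]
- Power, stratum included = Φ[d√(n/2)/√(1−R²) − 2.241]

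Here d√(n/2) is 2.995 at n = 185 and 2.785 at n = 160.

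| R² | Excess SE | n = 185: omitted → included | Cost (points) | n = 160: omitted → included | Cost (points) |
|---|---|---|---|---|---|
| 0 | 0% | 0.775 → 0.775 | 0 | 0.707 → 0.707 | 0 |
| 0.02 | 1.0% | 0.777 → 0.784 | 0.7 | 0.709 → 0.716 | 0.8 |
| 0.05 | 2.6% | 0.780 → 0.797 | 1.7 | 0.712 → 0.731 | 2.0 |
| 0.10 | 5.4% | 0.787 → 0.820 | 3.4 | 0.717 → 0.756 | 4.0 |

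With the stratum omitted, the true type I error at nominal 0.025 is 2[1 − Φ(2.241/√(1−R²))] = 0.0250, 0.0236, 0.0215 and 0.0181. It falls; it does not rise.

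**5. Check in a simulated GEE.** Three arms, 555 participants, Weeks 1–8 and 12, categorical time, exchangeable working correlation, participant-level sandwich SE, 400 trials per setting. Assumed: within-person correlation 0.6, half of participants on concurrent treatment, blocks of 3 and 6, R² defined per visit. SE with the stratum omitted, relative to included, for R² = 0, 0.02, 0.05 and 0.10:
- Week 12 contrast, complete data: 0.1%, 1.1%, 2.7%, 5.5% wider. With 20% dropout: 0.05%, 1.0%, 2.4%, 4.9%.
- Time-averaged group contrast: 0.1%, 1.7%, 4.3%, 9.0%. These are larger because R² is set per visit here, not for the contrasted outcome.
- Group-by-time interaction: 0.0% with complete data, at most 0.1% with 20% dropout. A covariate entered as a main effect cancels out of it.
- With a 20-clinic sandwich and working independence (300 trials per setting), Week 12 was 0.1%, 1.1%, 2.7% and 5.4% wider. The interaction was unchanged with complete data and at most 1.5% wider with dropout.

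**6. Cost if the stratum is not prognostic (R² = 0).** With balance, one extra degree of freedom costs 0.001 power points. Under chance imbalance (variance factor 1 + 1/(2n−3)) the loss is 0.12 points at n = 185 and 0.15 at n = 160.

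**The case against.** - **The interaction may be the main test.** Section 1.0 frames the Aim 2 main outcome as change over time by treatment, and Phase I was judged on the interaction. On that reading the precision gain is close to nil. This stands as a limit on the precision argument. But section 11.0 also lists time-point and overall contrasts, the sizing uses a t-test on pre-to-post change, and no single test is named as decisive. The prespecification point applies to all of them.
- **R² is assumed.** True. Nothing in the documents favours 0.05 or 0.10 over 0.
- **The power points depend on the base.** The GEE should be more powerful than the t-test. From an assumed base power of 0.90, the same formula gives costs of 0.4, 0.9 and 1.8 points for R² of 0.02, 0.05 and 0.10; from 0.95, 0.2, 0.5 and 1.0. The figures in the table are therefore illustrative.
- **The screen uses baseline data only.** So covariates are not chosen on outcome, and no bias or type I error inflation follows. That is correct and none is claimed.
- **The strata are not fully defined.** The plan does not say what counts as concurrent depression treatment, or which instrument and cut-points define the symptom stratum. This is a fair gap. It does not block the fix, since the value used to randomise must exist for each participant.

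**Conclusion.** The point holds, as a free improvement and not as a flaw that threatens the result. One of two stratification factors is absent from the primary model, the screen cannot be expected to supply it, and the screen leaves part of that model unfixed. These statements rest on the text alone.

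The size of the precision loss rests on an assumed R². Over 0 to 0.10, the SE of a time-point or overall group contrast is 0 to 5.4% too wide. The power cost is 0 to 3.4 points at 185 per arm or 0 to 4.0 at 160, and roughly half that if base power is 0.90. The interaction test is essentially unaffected.

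**What to change.** In section 11.0 (Aim 2, Efficacy):
- Delete the rule that adds significantly different baseline variables, and report baseline characteristics descriptively.
- Prespecify the covariates as baseline BDI-II (continuous), concurrent depression treatment as recorded for stratification, and sex. Keep the planned clinic clustering effect.
- State that the treatment covariate is the value at randomisation, not treatment obtained during follow-up, which is an outcome.
- If further demographics are of interest, name them in advance for a sensitivity analysis.

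Align the Quality Assurance text in section 12.0 for Aim 2. Say either that the Aim 3 adjustment rule is separate, or reconcile it in the same way.

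The cost is SAP wording only. Concurrent treatment status must already be recorded in order to stratify, so no new data are needed. If it turns out not to be prognostic, the power loss is under 0.01 points with balance and about 0.1 to 0.2 points under chance imbalance.

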#### Assessments

All participants will be text messaged and/or emailed a REDCap link, accessible via smartphone, to complete follow-up assessments weekly for 8 weeks, with a final follow-up at Week 12 (Figure 3). We utilized a similar assessment approach in the Moodivate Phase I feasibility trial with success—80% of participants completed at least half of all follow-up assessments and >50% completed all follow-up assessments. Assessments are estimated at 20 minutes each and participants will be compensated \$10 for completion of each. Participants can earn an additional \$40 for completing all follow-up assessments. All PCPs affiliated with the MUSC Primary Care ICCE will be invited to complete a brief study questionnaire at the beginning and end of the trial. Providers of patients enrolled in the Moodivate + EHR condition will be invited to complete an additional questionnaire following their patient's 12-week study follow-up assessment.

Aim 3: Cost-Effectiveness. The economic evaluation of Moodivate and Moodivate + EHR relative to TAU will be conducted from the budgetary perspective, as the primary focus herein is on the financial attractiveness of Moodivate for commercial launch. Health systems and payors in particular may be more likely to adopt Moodivate if it is established as either 1) cost-saving or 2) providing a clinical benefit cost-effectively. To examine cost-saving, we will first conduct a cost-benefit analysis by comparing changes in BDI-II scores and any reduction in all-cause and mental health-related healthcare expenditures prior to and following Moodivate implementation (or Moodivate + EHR) relative to TAU. Cost data for all inpatient, outpatient and emergency department (ED) care will be obtained from the MUSC Primary Care ICCE billings. As study participants may seek care outside of the MUSC system, we will also obtain all-payors' claims data from South Carolina's Revenue and Fiscal Affairs Office (RFA). RFA maintains data on inpatient and ED utilization across the state regardless of patients' point of care. The case for

Moodivate (with or without EHR) adoption and commercialization will be the strongest if the product reduces healthcare expenditures while also improving depressive symptoms.

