Feasibility and Acceptability. Within both the Moodivate and Moodivate + EHR groups, retention will be defined as the proportion of participants who use the app at least once within each week following enrollment. Retention point estimates and 95% confidence intervals (CIs) will be calculated for each group separately. A one-sided, one-sample proportion test will be used to determine whether retention is at least 70% (or higher) within each group. Other metrics of feasibility/acceptability (ease of use, continued desire to use, etc.) for both patients and providers will be summarized within group via summary statistics and 95% CIs, as appropriate.

Secondary Analyses. Secondary mediation analyses will examine whether changes in hedonic capacity, environmental reward, and/or behavioral activation mediate the relationship between treatment and change in depression. Following recommendations by Preacher and Hayes, bootstrapping will be used to examine the indirect effect of treatment on depression via change in proposed mediators. CIs around the indirect effect estimate that do not contain zero will be considered significant. Fit indices including  $\chi^2$ , the comparative fit index (CFI), the Tucker-Lewis index (TLI) and the root mean square error of approximation (RMSEA) will be examined. Model fit will be acceptable when  $\chi^2$  is nonsignificant, CFI and TLI are >  $0.9^{76,77}$  and RMSEA is  $< 0.05^{78}$ .

Adverse Events (AEs). AEs will be defined as a clinically significant (i.e., 10-point) increase in depressive symptoms on the BDI-II from baseline or any incidence of suicidality (response of "I would like to kill myself" or "I would kill myself if I had the chance" on the BDI-II suicidality item). We will determine the

incidence of AEs and associated 95% CIs. A chi-square test will determine if the rate of AEs is greater than 5% in any group.

#### Data Analytic Plan for Aim 3

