The economic evaluation of Moodivate and Moodivate + EHR relative to TAU will be conducted from the budgetary perspective, as the primary focus herein is on the financial attractiveness of Moodivate for commercial launch. Health systems and payors in particular may be more likely to adopt Moodivate if it is established as either 1) cost-saving or 2) providing a clinical benefit cost-effectively. To examine cost-saving, we will first conduct a cost-benefit analysis by comparing changes in BDI-II scores and any reduction in all-cause and mental health-related healthcare expenditures for a 12-month period before and after Moodivate implementation (or Moodivate + EHR) relative to TAU. Cost data for all inpatient, outpatient and emergency department (ED) care will be obtained from the MUSC primary care ICCE billings department. As study participants may seek care outside of the MUSC system, we will also obtain all-payors' claims data from South Carolina's Revenue and Fiscal Affairs Office (RFA). RFA maintains data on inpatient and ED utilization across the state regardless of patients' point of care. The case for Moodivate (with or without EHR) adoption and commercialization will be the strongest if the product reduces healthcare expenditures while also improving depressive symptoms.

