#### Regulatory Issues

This study will be registered on clinicaltrials.gov. The study does not require an IND from the FDA. All serious AEs will be reported to the MUSC Committee on Human Research within 48-hours. Follow-up of all unexpected and serious AEs will also be reported. All AEs will be reviewed weekly by the PI and yearly by the IRB. Any significant actions taken by the local IRB and protocol changes will be relayed to the funding agency. We estimate the significant AE rate to be very low (< 5%). If monthly monitoring indicates the rate is above this, we will convene a meeting of the DSMB. Potential conflicts of interest (COI) will be reported using the rules of MUSC's COI committee.

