#### Trial Safety

The potential risks and benefits and methods to minimize these risks are outlined in the "Protection of Human Subjects" section. We will determine if any AEs result in dropouts or are serious according to FDA guidelines. The PI ([name]) will serve as the Program Manager for AEs. All unexpected AEs will be monitored while they are active to determine if treatment is needed. We anticipate that AEs will be rare given that the Moodivate app is non-invasive and that all participants will be engaged with current healthcare. Nonetheless, any AEs will be coded on a weekly basis using the FDA's COSTART rules and entered into a database. For each weekly study meeting, the research assistant will prepare a summary of all AEs, including their severity, whether they caused a dropout, required treatment, and presumed relation to app utilization. The PI will review this at the weekly study meeting (or before if more urgent). At the weekly meeting (or before if urgent), the research assistant will report any premonitory symptoms to suggest emergence of a serious psychiatric condition (e.g., suicidality). Drs. [name] and [name], board-certified Family Medicine physicians, will be available on an ad-hoc basis for on-site medical supervision for any issues that cannot be resolved by [name].

Study procedures will follow as much as possible the FDA's Good Clinical Practice Guidelines and our research team has found Spilker's comprehensive text on conducting clinical trials to be useful. We will encourage participants to notify their physicians that a) they are in a randomized controlled research study examining a treatment for depressed mood, and b) the physician should contact the PI directly if the physician has any questions.

The research assistants will be instructed not to reveal whether a person is a participant in the study and will report to the PI any outside requests for information about a participant or any breaches in confidentiality. All requests by participant's physicians and other medical providers will be referred directly to the PI.

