# 13.0 Risks to Subjects

The potential risks in this study include those related to: a) depressive symptoms, b) clinical deterioration, c) confidentiality, d) potential data breach from the app database, and e) frustration. All risk mitigation strategies outlined below were approved by the MUSC IRB and implemented with success during our Phase I trial.

- a) Depressive symptoms: Depressive symptoms will be monitored via the BDI-II. All participants will complete the BDI-II weekly online via a REDCap survey that is accessible via mobile phone web browsers. All participants will own smartphones. Thus, all participants should have access to the online BDI-II assessments.

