- b) Clinical deterioration: [name] and her research team will monitor participant PHQ-9 and BDI-II scores for possible clinical deterioration (i.e., increasing depressive symptoms and/or the development of suicidal ideation) throughout the course of the study as participants complete the PHQ-9 and BDI-II weekly. Clinical deterioration will be defined as an increase of 10 or more points on the BDI-II from the baseline BDI-II assessment or a response of "I would like to kill myself" or "I would kill myself if I had the chance" on the suicidal thoughts or wishes item of the BDI-II. Our team has developed alerts within REDCap reports that the investigative team checks daily to determine whether a participant completed a BDI-II assessment and evidenced evidences clinical deterioration. This system has now been implemented with success across multiple studies. In the event that a participant evidences clinical deterioration, [name] will contact the participant via phone and will provide referrals for local mental health resources for depression treatment. [name] will suggest that the participant seek treatment and then will follow-up with the participant via phone one week later. In the event that a participant reports suicidal ideation either during study screening or during subsequent assessments. [name] will 1) page the participant's attending primary care provider and 2) complete a risk assessment with the participant via phone. [name] will query the participant for details regarding the suicidal ideation, including a likelihood of harming oneself imminently and a plan for committing suicide. If the participant reports an imminent likelihood of harming him/herself or a plan for committing suicide, [name] will call emergency services and will remain on the phone with the participant until emergency services arrive. Contact information including home address will be collected during study screening and will be provided if necessary to emergency services personnel. [name] is a licensed clinical psychologist and has more than 10 years of experience conducting suicide risk assessments. In the event that a participant evidences clinical deterioration, the participant will be allowed to continue in the trial, but we will recruit an additional participant for data collection purposes.

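### The planned adverse-event statistics count only BDI-II answers and do not match the wider serious-AE framework in Section 12.0, which has no planned by-arm analysis

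*Combined protocol and SAP*

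**What the plan says.** **The analysed definition.** Section 11.0 (Data Analytic Plan for Aim 2, Adverse Events) is the only explicit AE definition: "AEs will be defined as a clinically significant (i.e., 10-point) increase in depressive symptoms on the BDI-II from baseline or any incidence of suicidality". A bracket then limits suicidality to two specific responses on the BDI-II suicidality item. The plan is to report incidence with 95% CIs, and "A chi-square test will determine if the rate of AEs is greater than 5% in any group". No alpha, sidedness, denominator or missing-data rule is given for this analysis.

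**The data source.** Section 13.0 says "All participants will complete the BDI-II weekly online via a REDCap survey". It defines deterioration by the same instrument and the same threshold: "Clinical deterioration will be defined as an increase of 10 or more points on the BDI-II from the baseline BDI-II assessment". The Assessment Grids in Section 4.0 list no AE form and no question on hospital care.

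**The oversight framework.** Section 12.0 is broader. Under Regulatory Issues, "All serious AEs will be reported to the MUSC Committee on Human Research within 48-hours". Under Trial Safety, "We will determine if any AEs result in dropouts or are serious according to FDA guidelines"; AEs are also coded weekly with COSTART and summarised by severity, dropout, treatment needed and relation to the app. The yearly monitoring report covers AEs, unexpected AEs and serious AEs. The DSMB reviews AEs and can be convened for unexpected serious ones.

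**Other data.** The Data Analytic Plan for Aim 3 notes that "RFA maintains data on inpatient and ED utilization across the state regardless of patients' point of care". These data are planned only for the cost analysis.

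**The concern.** Section 2.0 (third reason for a further trial) says that a larger trial is needed to evaluate safety comprehensively, partly to support an FDA path. In a depression trial, the outcomes a safety reader looks for first are suicide attempts, psychiatric admissions and deaths. None of these is a BDI-II response, so none counts in the AE statistics in its own right. Section 12.0 plainly expects serious and unexpected events, yet nothing in it says how they will be tabulated by arm or on what denominator.

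Ascertainment is a second issue. If AEs come only from returned surveys, the reported incidence depends partly on how many surveys are returned. Worsening that begins after a participant stops responding cannot be recorded. The final report could give an AE rate that follows the plan exactly and still says little about serious harm.

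**Working it through.** The plan states no AE figure to reproduce. The check is a reading of the sections side by side, followed by an illustration of how far survey-only ascertainment could matter.

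**1. What each section would capture**

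| Event | AE statistics (Section 11.0) | Oversight (Sections 12.0 and 13.0) |
|---|---|---|
| 10-point BDI-II rise on a returned survey | Counted | Reviewed; may be graded serious |
| Qualifying suicidality response on a returned survey | Counted | Reviewed; may be graded serious |
| Suicide attempt, psychiatric ED visit or admission, or death, with no qualifying survey | Not counted | Reportable and reviewable if the team learns of it |
| Worsening recorded before dropout | Counted | Reviewed; AE-related dropout is noted |
| New worsening after the last returned survey | Not counted | Seen only if reported by another route |

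No active route other than the surveys is specified for finding such events.

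**2. How many participants could be affected**

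Inputs, from Sample Size Estimation: 20% attrition and 200 per group, with a total of 695.

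- Stated group size: 0.20 × 200 = 40.
- Equal split of 695: 695/3 ≈ 232, and 0.20 × 232 ≈ 46.

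On Phase I survey completion, Section 10.0 (Assessments) reports that 80% completed at least half of the follow-ups and ">50% completed all follow-up assessments".

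**3. Effect of unobserved participants on the rate**

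Assumptions: attrition means no follow-up BDI-II at all (a worst case), and 8 AEs are seen among 200 − 40 = 160 responders. Let r be the AE proportion in the 40 not observed.

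- Observed rate: 8/160 = 5.0%.
- Rate in all randomised: (8 + 40r)/200.

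| r | Rate in all 200 |
|---|---|
| 0 | 8/200 = 4.0% |
| 0.10 | 12/200 = 6.0% |
| 0.20 | 16/200 = 8.0% |
| 0.30 | 20/200 = 10.0% |
| 1 | 48/200 = 24.0% |

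The same observed data fall on either side of the plan's 5% threshold, depending on r and on the denominator, and the plan fixes neither.

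**4. Effect on the 5% test**

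Assumption: one-sided exact test at alpha 0.05, because the plan does not specify. If the true rate is 10%, power to show a rate above 5% is 86% with n = 200 (16 or more events needed) and 74% with n = 160 (14 or more).

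**5. Sensitivity of the BDI-II component to survey count**

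Illustration only. Mean change falls linearly to −7.8 (the Phase I TAU figure) by Week 8 and then stays flat. The assumed SD is 10.5 to 15 and the assumed within-person correlation is 0.6 to 0.8. The probability of recording a rise of at least 10 points is about 24–49% with all nine surveys, 23–45% with the first five, and 15–23% with Week 1 only. If the SD instead rises linearly from half its final value (again assumed), the figures are about 11–35% with nine surveys and 2–7% with one. Fewer surveys always give fewer chances to record an event. The levels and the size of the gap depend on the assumptions, and the model says nothing about attempts, admissions or deaths.

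**The case against.** The strongest reply is that Section 12.0 already covers serious events. It provides FDA seriousness grading, COSTART coding, IRB reporting within 48 hours, yearly reports and DSMB review. Coding and an unexpected category would make little sense if only two BDI-II criteria counted. This stands as far as oversight goes. A reader might infer that attempts, admissions and deaths escape all safety review, and the documents do not support that. Section 12.0 does not, however, supply a by-arm table, a denominator or a collection method.

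Three other strong readings also fail:

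- **That the BDI-II definition cannot yield serious or dropout-causing AEs.** It can: a 10-point worsening may precede dropout, and Protections Against Risk speaks of serious or severe AEs related to deterioration.
- **That all harm in non-responders is lost.** Events before dropout are counted, AE-related dropout is recorded, and the Missing Data paragraph assesses differential attrition by group.
- **That an arm with fewer returned surveys would pass a formal comparison as safer.** No between-arm AE test is planned. Each group is tested against 5%, so the risk lies in informal comparison of the rates.

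It is also fair to say that safety is not among the main outcomes named for Aim 2, and that in the first version of the illustration the first five surveys capture most recordable BDI-II events. Both points limit the severity but leave the mismatch between Sections 11.0 and 12.0 in place.

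**Conclusion.** The point holds as a mismatch between sections. The planned AE statistics rest on BDI-II answers alone. Serious and unexpected AEs are overseen under Section 12.0 but have no planned by-arm analysis. An attempt, psychiatric ED visit or admission, or death enters the statistics only through a qualifying returned survey, and new harm after non-response is not counted.

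The definitional gap needs no numerical assumption. The ascertainment range does: 4% to 24% around an observed 5% assumes 8 events and no BDI-II from any of 40 participants in a group of 200. The simulated percentages are illustrative only. Severity is should-fix: oversight of serious events exists, but following the analysis plan as written would fall short of the comprehensive safety evaluation that Section 2.0 calls for.

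**What to change.** Reconcile the Adverse Events paragraph of Section 11.0 with Section 12.0, and analyse two components.

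- **(a) BDI-II-defined events.** Keep them under their own label. Report them on all randomised participants and also on those with at least one follow-up BDI-II, and show the number of completed surveys by arm. The second set is selected by response after randomisation, so it should not stand alone.
- **(b) Serious AEs.** Add a descriptive by-arm tabulation on all randomised participants, including suicide attempts, psychiatric ED visits or admissions, and known deaths. Take these from Section 12.0 reports, the MUSC EHR and the inpatient/ED data already planned for Aim 3, and name the sources in the plan.

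State the denominator, alpha and sidedness for the 5% test.

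**Cost.** Protocol and SAP wording, an EHR query and some case review; no new participant assessments. The claims data arrive late, so they serve the final analysis and not ongoing monitoring. They may miss deaths outside hospital, and permission to use them for safety must be confirmed.
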